7.2 General statistical considerations

Descriptive statistics (e.g. mean, median, standard deviation (SD), minimum (MIN), maximum (MAX), and number of subjects with an observation (N) or missing observation (NMISS)) are used for summarizing continuous variables. Additional statistics will be provided for PK-related data, including the geometric mean, SD of log-transformed data, geometric CV%.

Frequencies and percentages are used for summarizing categorical variables.

All summary statistics will be presented by treatment arm and if repeated measures, then by visit/collection time point.

All listings will be created using ITT population. The PP and ITT flags for each subject will be included in all listings.

All tests will be two-sided, if not stated differently. P-values smaller than 0.05 will be considered statistically significant, if not stated otherwise. In addition to the inferential statistics, 95% confidence intervals will be constructed. For the primary endpoint for each of the dose levels a 95% confidence interval of the treatment difference will be constructed. Ninety-five percent (95%) confidence intervals will be constructed for the individual treatment point estimates.

Various covariates (baseline values, site and sex) will be included in the models to increase sensitivity of the tests and will be retained in the respective models regardless of their significance or lack thereof.

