RBC	Red blood cell
RCD-II	Type II Refractory Celiac Disease
RE	Role limitations due to emotional problems
SAE	Serious adverse event
SAP	Statistical analysis plan
SC	Subcutaneous
sCD3-	Surface CD3-negative
sCD8-	Surface CD8-negative
SD	Standard deviation
SOC	System organ class
ULOQ	Upper limit of quantification
UN	Unstructured
VT	Vitality
VH:CD	Villous height to crypt depth ratio

WBC White blood cell

WHO DD World Health Organization Drug Dictionary

1 Introduction

This is a statistical analysis plan (SAP) for study CELIM-NRCD-001 which is based on the final study protocol CELIM-NRCD-001 Version 3 (dated 29AUG2016). This SAP describes the statistical analyses which will be presented in the clinical study report.

2 Study objectives

The study objectives are the following:

The **primary objective** of the study is:

- To assess the efficacy of AMG 714 in attenuating the effects of gluten exposure in adults with celiac disease.

The **primary efficacy endpoint** is:

- Attenuation of gluten-induced small intestinal mucosal morphological injury, measured morphometrically as villous height to crypt depth (VH:CD) ratio.

The primary endpoint of the study is the difference in the Baseline-to-Week-12 % change of VH:CD ratio between each of the two AMG 714 dose arms against the placebo arm.

The **secondary efficacy endpoints** of the study are:

- Attenuation of gluten-induced small intestinal mucosal inflammation measured as intraepithelial lymphocyte (IELs) density;
- Attenuation of gluten-induced small intestinal mucosal morphological injury using a grouped classification of Marsh score;
- Attenuation of gluten-induced serum antibodies (i.e. anti-tissue transglutaminase antibodies [anti-tTG] IgA, anti-deamidated gliadin peptide antibodies [anti-DGP] IgA and IgG);
- Attenuation of gluten-induced clinical symptoms (i.e. Bristol Stool Form Scale [BSFS], Gastrointestinal Symptom Rating Scale [GSRS] and celiac disease GSRS [CeD-GSRS]).

The secondary endpoints of Marsh score and total IEL counts will be evaluated by the change from baseline to Week 12 between the two AMG 714 dose arms and the placebo arm. Anti-tTG IgA, anti-DGP IgA and IgG will be evaluated by comparing the change from baseline in results obtained after every four weeks of two AMG 714 dose arms and placebo arm. BSFS, GSRS and CeD-GSRS will be evaluated by comparing the change from baseline in weekly scores of two AMG 714 dose arms and placebo arm.

The **secondary objective** of the study is:

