The primary endpoint of the study is the difference in the Baseline-to-Week-12 % change of VH:CD ratio between each of the two AMG 714 dose arms against the placebo arm.

The primary endpoint will be tested for each of the two dose levels, 150 mg or 300 mg, separately as follows:

$H_{10}: \mu_{AMG\ 714\ (300mg)} = \mu_{Placebo}$
against the alternative

$H_{11}: \mu_{AMG\ 714\ (300mg)} \neq \mu_{Placebo}$
and

$H_{20}: \mu_{AMG\ 714\ (150mg)} = \mu_{Placebo}$
against the alternative

$H_{21}: \mu_{AMG\ 714\ (150mg)} \neq \mu_{Placebo}$

where $\mu_{AMG\ 714\ (300mg)}$, $\mu_{AMG\ 714\ (150mg)}$ and $\mu_{Placebo}$ denote the mean Baseline-to-Week-12 % change of VH:CD ratio in the high dose, low dose and placebo arm, respectively. Each of the two hypotheses will be tested using a two-sided, 0.05 level of significance without any adjustments for multiple comparisons.

6 Estimation of sample size

The sample size of approximately 63 subjects (21 subjects/arm) has been calculated to achieve at least ~ 80% power in the primary endpoint, the difference in the Baseline-to-Week-12 %-change of VH:CD ratio between the two AMG 714 arms and the placebo arm. This sample size provides close to 90% (88.8%) power to detect a 40-point difference between the placebo arm and the 300mg high-dose arm, and close to 80% (79.3%) power to detect a 35-point difference between the placebo arm and the 150mg low-dose arm.

This sample size calculation is based on the following assumptions:

- Two-sided type one error rate $\alpha = 0.05$.
- Power $1-\beta = 80\%$.
- Analysis method: one-way ANOVA by SAS® (proc power).
- Common SD = 36 for the baseline to Week 12 %-change in VH:CD.
- 45%-change (decrease) in the placebo group, %-change (decrease) of 10% in the 150mg and 5% in the 300mg arms.
- Drop-out rate ~19% (assuming non-evaluable drop-outs plus DH $\leq 15\%$ and non-evaluable due to technical issues or villous atrophy at baseline $< 5\%$).

These assumptions are based on the observations made in a similar 12-week gluten challenge study done with 3-5 grams of gluten per day (Lähdeaho *et al*, 2011). According to this sample size calculation (including a 19% drop-out rate), 17 completed evaluable subjects/arm (51 subjects in total) will be needed for the primary analysis.

7 Statistical methods

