Due to the repeated structure of the data, the measurements within a subject will be correlated. Therefore, it is assumed that the overall covariance matrix of the response is block-diagonal. In order to determine the covariance structure that best fits the data, the same model with different covariance structures is fitted. Initially, models will be fit assuming unstructured (UN) variance-covariance structure. Common within and between treatment variance components (compound symmetry (CS), first-order autoregressive (AR(1)) and Toeplitz covariance structures) will be further explored to increase sensitivity of statistical tests. The best model will be chosen by comparing the Akaike Information Criterion (AIC) of the models with different covariance structures.

The following SAS program will be used for carrying out the analysis:

```

proc glimmix data=gsrs;
  class subjid trt site sex week(ref=FIRST);
  model gsrs = gsrs_bl trt site sex week trt*week / solution;
  random _residual_ / subject=subjid type=UN;
  estimate "150 mg AMG 714 vs Placebo" trt 1 0 -1 /alpha=0.05 cl;
  estimate "300 mg AMG 714 vs Placebo" trt 0 1 -1 /alpha=0.05 cl;
  estimate "Week 1: 150 mg AMG 714 vs Placebo" trt 1 0 -1
    trt*week 0 0 0 0 0 0 0 0 0 0 0 0 0 0 0 0 1
    0 0 0 0 0 0 0 0 0 0 0 0 0 0 0 0 0
    0 0 0 0 0 0 0 0 0 0 0 0 0 0 0 0 -1 /alpha=0.05 cl;
  estimate "Week 1: 300 mg AMG 714 vs Placebo" trt 0 1 -1
    trt*week 0 0 0 0 0 0 0 0 0 0 0 0 0 0 0 0 0
    0 0 0 0 0 0 0 0 0 0 0 0 0 0 0 0 1
    0 0 0 0 0 0 0 0 0 0 0 0 0 0 0 0 -1 /alpha=0.05 cl;
  estimate "Week 2: 150 mg AMG 714 vs Placebo" trt 1 0 -1
    trt*week 1 0 0 0 0 0 0 0 0 0 0 0 0 0 0 0 0
    0 0 0 0 0 0 0 0 0 0 0 0 0 0 0 0 0
    -1 0 0 0 0 0 0 0 0 0 0 0 0 0 0 0 0 /alpha=0.05 cl;
  ...
  estimate "Week 16: 300 mg AMG 714 vs Placebo" trt 0 1 -1
    trt*week 0 0 0 0 0 0 0 0 0 0 0 0 0 0 0 0 0
    0 0 0 0 0 0 0 0 0 0 0 0 0 0 0 0 1 0
    0 0 0 0 0 0 0 0 0 0 0 0 0 0 0 0 -1 0 /alpha=0.05 cl;
  lsmeans trt /alpha=0.05 cl;
  lsmeans trt*week /alpha=0.05 cl;
  ods output CovParms=Cov_Par LSMeans=LS_est Estimates=Eff_est
    FitStatistics=Fit_Stat ParameterEstimates=Par_est
    Tests3=Type_3;
run;

```

Note that the value of `type` will be changed according to which covariance structure is being fitted.

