The absolute change from baseline in CeD-GSRS will be analysed using a linear mixed effects repeated measures model (MMRM) with the baseline value, treatment group, site, sex, time point and a time point-by-treatment group interaction term as fixed effects with an underlying correlation structure between the time points that results in the best fit for the model. Subject will be included as a random effect. The following model will be fitted:

$$Y_{ijklm} = \mu + \tau_j + \varphi_k + \alpha_l + \gamma_m + \lambda_{lm} + \beta \cdot \text{baseline CeD GSRS}_{ijklm} + \eta_i + \varepsilon_{ijklm},$$

where

Y_{ijklm} is the absolute change from baseline in total CeD-GSRS score for subject i ($i = 1, \dots, n_{jkl}$) from site j ($j = 1, 2, 3$), sex k ($k = 1, 2$) and treatment group l ($l = 1, 2, 3$) at week m ($m = 1, \dots, 16$),

μ is the overall mean,

α_l is the fixed effect due to treatment l ,
 φ_k is the fixed effect due to sex k ,
 τ_j is the fixed effect due to site j ,
 γ_m is the fixed effect due to time point m ,
 λ_{lm} is the fixed interaction effect due to treatment l and time point m ,
 β is the parameter estimate of the baseline total CeD-GSRS score,
 η_i is the random effect due to subject i ,
 ε_{ijklm} is the random error for subject i from site j ($j = 1, 2, 3$), sex k ($k = 1, 2$) and treatment group l for time point m .

Due to the repeated structure of the data, the measurements within a subject will be correlated. Therefore, it is assumed that the overall covariance matrix of the response is block-diagonal. In order to determine the covariance structure that best fits the data, the same model with different covariance structures is fitted. Initially, models will be fit assuming unstructured (UN) variance-covariance structure. Common within and between treatment variance components (compound symmetry (CS), first-order autoregressive (AR(1)) and Toeplitz covariance structures) will be further explored to increase sensitivity of statistical tests. The best model will be chosen by comparing the Akaike Information Criterion (AIC) of the models with different covariance structures.

The following SAS program will be used for carrying out the analysis:

```

proc glimmix data=ced_gsrs;
  class subjid trt site sex week(ref=FIRST);
  model ced_gsrs = ced_gsrs_bl trt site sex week trt*week / solution;
  random _residual_ / subject=subjid type=UN;
  estimate "150 mg AMG 714 vs Placebo" trt 1 0 -1 /alpha=0.05 cl;

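### Section 7.2 calls any p<0.05 statistically significant, while the weekly and visit models of the symptom and antibody endpoints yield 10 to 36 contrasts each with none named as deciding

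*SAP*

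**What the plan says.** Section 7.2 of the SAP gives the general rule: "All tests will be two-sided, if not stated differently", and "P-values smaller than 0.05 will be considered statistically significant, if not stated otherwise". Nothing in section 7.6.2 states otherwise for a secondary endpoint. The open waiver in section 5, where hypotheses are "tested using a two-sided, 0.05 level of significance without any adjustments for multiple comparisons", refers to the two primary comparisons only.

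Section 2 lists symptoms as one secondary endpoint measured on three scales and sets the time frame: "BSFS, GSRS and CeD-GSRS will be evaluated by comparing the change from baseline in weekly scores". Antibodies are compared every four weeks. IEL density and Marsh score are compared at Week 12 only.

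The SAS code in section 7.6.2 turns this into contrasts. For GSRS it asks for one overall contrast per dose and then one per dose per week, from "Week 1: 150 mg AMG 714 vs Placebo" through the 300 mg contrast at Week 16. CeD-GSRS follows the same pattern. BSFS runs from Week 0 to Week 16. Each antibody model covers Visits 3, 5, 7 and 8. No week, visit or overall contrast is identified as the one on which an endpoint is judged.

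Under section 3, active gluten is taken from Visit 2 (Week 2) to Visit 7 (Week 12).

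**The concern.** Attaching the words statistically significant to every p<0.05 is harmless when an endpoint has one contrast per dose. It is not harmless when an endpoint has 34 or 36 and the plan does not say which one counts. After unblinding, any week that crosses 0.05 may be reported as a significant difference in symptoms, and the SAP would allow the label. Some of those weeks fall before the challenge begins or after it has ended, although the endpoint is attenuation of gluten-induced symptoms. The overall contrast also averages over those weeks.

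At stake is how far a reader can rely on a significant symptom or antibody result in the study report. The primary endpoint is not touched.

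**Working it through.** **1. The plan's own figure.** The SAP gives no error rate for the secondary contrasts, so its primary power was reproduced to confirm the sample size and degrees of freedom. Inputs (section 6): 17 evaluable per arm, SD 36, differences of 40 and 35 points, two-sided 0.05, one-way ANOVA. Standard error = 36 × √(2/17) = 12.35; noncentrality = 40/12.35 = 3.24 and 35/12.35 = 2.83; error df = 3 × 17 − 3 = 48. Power is 88.76% and 79.32%, against the stated 88.8% and 79.3%. The same 17 per arm is used below.

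**2. Counting contrasts** (leading models, one per-protocol set; time points × 2 doses + 2 overall).

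| Endpoint | Contrasts | Time-specific contrasts outside Weeks 2–12 |
|---|---|---|
| GSRS, Weeks 1–16 | 16 × 2 + 2 = 34 | Weeks 1, 13–16: 10 of 32 |
| CeD-GSRS, Weeks 1–16 | 34 | 10 of 32 |
| BSFS, Weeks 0–16 | 17 × 2 + 2 = 36 | Weeks 0, 1, 13–16: 12 of 34 |
| anti-tTG IgA | 4 × 2 + 2 = 10 | Visit 8: 2 of 8 |
| anti-DGP IgA and IgG | 2 × 10 = 20 | Visit 8: 2 of 8 each |

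This makes 134. IEL and Marsh add 2 each, at Week 12 only, for 138. With no drug effect, 134 × 0.05 = 6.7 of the repeated-measures contrasts are expected below 0.05, whatever their correlation. The absolute-change repeats for GSRS and anti-tTG and the second per-protocol population come on top.

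**3. Ceiling.** If contrasts were independent, the chance of at least one p<0.05 would be 1 − 0.95^34 = 82.5% for GSRS and 1 − 0.95^10 = 40.1% for one antibody. Weeks within a subject are correlated and both doses share the placebo arm, so the true values are lower.

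**4. One symptom scale, simulated.** No drug effect, three arms of 17, complete data, pooled-variance t tests on 48 df, 34 contrasts. The correlation is an assumption, since the SAP gives none.

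| Assumed within-subject correlation | At least one p<0.05 |
|---|---|
| AR(1) 0 / 0.5 / 0.7 / 0.8 / 0.9 / 0.95 | 79 / 73 / 65 / 58 / 43 / 32% |
| Exchangeable 0.3 / 0.5 / 0.6 / 0.7 / 0.8 / 0.9 | 70 / 58 / 51 / 43 / 35 / 26% |
| Random intercept share 0.2 / 0.4 / 0.6 / 0.8 plus AR(1) 0.6 | 63 / 54 / 43 / 32% |

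Counting only results in favour of drug, the range is 13–53%.

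**5. Adding the planned baseline covariate.** The GSRS and CeD-GSRS models adjust for baseline, which removes much of the stable between-subject correlation. Under exchangeable correlation r, the correlation left after adjustment is (r − r²)/(1 − r²) = r/(1 + r), which cannot exceed 0.5. The low figures at high exchangeable correlation in step 4 therefore do not apply to these two models. With the covariate, GSRS gives about 44–73%, or 24–43% in favour of drug only.

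**6. Three symptom scales together.** GSRS and CeD-GSRS were assumed strongly correlated (0.90–0.95) and BSFS correlated 0–0.5 with them. With the covariate for GSRS and CeD-GSRS, at least one p<0.05 occurs in about 67–94% of trials, and 38–70% in favour of drug. Without it, the lowest value found was 46% (exchangeable 0.9) and the highest 96%; in favour of drug, 25–70%.

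**7. One antibody** (10 contrasts): 16–34%.

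**8. With one fixed contrast per dose.** A single scale gives about 9% if both doses are tested freely, and 5% if 150 mg is tested only after 300 mg succeeds. Across the three symptom scales it is about 10–12% with 300 mg first and 18–21% with both doses tested freely.

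The simulations treat BSFS as normal with 16 weeks, although the SAP models it as Poisson counts over 17. They also leave out missing data and the choice of covariance structure by AIC.

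**The case against.** The strongest reply is that the SAP never says an endpoint is met if any one contrast falls below 0.05. Formal hypotheses exist only for the primary endpoint, and the outputs listed in section 7.6.2 are estimates, marginal means and confidence intervals. That is correct: a reader might infer a success rule of that kind, but none is written. What stands is narrower. Section 7.2 supplies the significance label for any p-value, and nothing withholds it from the weekly contrasts.

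A second reply is that each model already has an overall contrast per dose, listed first in the code, which could serve as the main result. It could, but the SAP does not say so, and it averages over weeks outside the challenge.

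Third, this is a Phase 2a study that openly forgoes adjustment even for its two primary tests. That stance can justify unadjusted secondary p-values. It does not settle which of 34 or 36 contrasts per scale is to be read as the result.

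Fourth, an endpoint of attenuation is not supported by a week that favours placebo, so two-directional counts overstate the risk of a false claim of benefit. This stands, and it is why the figures in favour of drug are given separately.

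**Conclusion.** The point holds for the repeated-measures secondary endpoints. With no drug effect and 17 per arm, the chance of at least one contrast that section 7.2 would call significant is roughly 25–80% for a single symptom scale, roughly 45–95% for the three scales together and 16–34% for one antibody. All of these rest on an assumed within-subject correlation, and the three-scale figures also on assumed correlations between scales.

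Three stronger readings are not supported:

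- **That a false positive occurs in most trials.** A single scale passes 50% only under some correlations, and the three-scale chance in favour of drug can be as low as about 25%.
- **That all secondary endpoints are affected.** IEL density and Marsh score have one time point, and the antibody models are affected less.
- **That the symptom and antibody data cannot inform on attenuation.** Estimates and intervals over time remain informative. The fault lies in the label and the missing deciding contrast.

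**What to change.** Before unblinding, name in section 7.6.2 one deciding contrast per dose for each of GSRS, CeD-GSRS, BSFS, anti-tTG IgA, anti-DGP IgA and anti-DGP IgG. Week 12 (Visit 7) is one option because it matches the primary endpoint, with 300 mg against placebo tested first and 150 mg next.

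In section 7.2, state that all other weekly, visit, overall, absolute-change and PP2 p-values for the secondary endpoints are nominal and descriptive and will not be called statistically significant.

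The cost is a few sentences and a table footnote. No model, table or data collection changes. The small downside is that an isolated weekly p<0.05 can no longer be reported as significant. The fix does not control error across all secondary endpoints: even with 300 mg first, about 10–12% remains across the three symptom scales.

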7.2.1 Definition of derived variables

Geometric mean will be calculated as:

$$\text{mean}_{\text{geo}} = \sqrt[n]{x_1 x_2 \cdots x_n} = \exp\left\{\frac{1}{n} \sum_{i=1}^n \ln x_i\right\}.$$

Values that are missing or not available will be ignored in calculation of geometric mean.

CV%_{geo} will be calculated using the following formula:

$$\text{CV\%}_{\text{geo}} = 100\% \cdot \sqrt{\exp V_{\ln} - 1}.$$

Values that are missing or not available will be ignored in calculation of CV%_{geo}.

Absolute change from baseline for a given treatment needs to be calculated, the following formula will be used:

$$\text{Absolute change from baseline} = \text{Post-baseline value} - \text{Pre-dose value}.$$

For weekly scores, Week 0 score is considered to be the baseline value. If Week 0 score is not available, the first non-missing result within 2 weeks of treatment will be used as baseline. For daily scores (e.g. CeD PRO), Day 0 score is considered to be the baseline, in case Day 0 score is not available, the first non-missing result within 2 weeks of treatment will be used as baseline. Otherwise, the given subject will be considered non-evaluable for the specific test. In case pre-dose value doesn't exist (i.e. for biopsy endpoints), screening value will be used as baseline.

In the case where relative (%) change from baseline needs to be calculated, the following formula will be used:

$$\text{Relative (\%)} \text{ change from baseline} = (\text{Post-baseline value} - \text{Pre-dose value}) / (\text{Pre-dose value}) \cdot 100\%.$$

For weekly scores, Week 0 score is considered to be the baseline value. If Week 0 score is not available, the first non-missing result within 2 weeks of treatment will be used as baseline. For daily scores (e.g. CeD PRO), Day 0 score is considered to be the baseline, in case Day 0 score is not available, the first non-missing result within 2 weeks of treatment will be used as baseline. Otherwise, the given subject will be considered non-evaluable for the specific test. In case pre-dose value doesn't exist (i.e. for biopsy endpoints), screening value will be used as baseline.

Body mass index (BMI) is calculated using the formula:

$$\text{BMI (kg/m}^2\text{)} = \text{weight (kg)} / [\text{height (m)} * \text{height (m)}].$$

Body surface area (BSA) is calculated using Dubois' formula:

$$\text{BSA (m}^2\text{)} = 0.007184 * \text{height (cm)}^{0.725} * \text{weight (kg)}^{0.425}.$$

Table 2 Decimal places for summary statistics of continuous and categorical variables

Statistic	Number of digits
Minimum, maximum	Same as in original data
Mean, median, mean_{geo}	1 more than in original data
SD, SD_{geo}	2 more than in original data
Frequencies (%)	1 decimal place
CV\%_{geo}	1 decimal place

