Subjects' adherence to GFD and consumption of provided gluten will be periodically assessed via stool and urine sample testing using the iVYELISA GIP stool and urine gluten tests. Subjects with known or suspected GFD transgressions or those suspected of non-compliance to protocol specified gluten dosing will be counselled and allowed to continue in the study.

A study site staff member will contact each subject by telephone both one day and one week after the first study drug administration in order to assess for AEs. Subjects will return to the clinic every two weeks for study drug administration and/or efficacy and safety assessments as indicated in the study schedule of events in [Appendix 1](#). The final study drug administration will occur at Visit 6 (Week 10/Day 70). An end-of-study efficacy assessment

will be collected at Visit 7 (Week 12/Day 84). A final study visit will be conducted six weeks after the last administration of study drug at Week 16 (Visit 8/Day 112).

Subjects who meet all other study entry criteria will undergo upper gastrointestinal endoscopy and biopsy prior to baseline (Visit 1, Week 0/Day 0) and at the end of the 12-week randomized period while still on the gluten challenge within five days before Visit 7 (Week 12/Day 84) in order to assess changes from baseline in VH:CD ratio, IELs, and Marsh score.

If the screening biopsy shows villous atrophy with a VH:CD less than 1.5 (1.4 or lower), and after notification to the sponsor, the subject may be allowed to stay in the study but the gluten challenge will not be started (or will be interrupted if the patient has been started in the challenge) and the subject will be analysed separately for the main efficacy assessments (primary and secondary endpoints). Subjects with VH:CD 1.5 or above will receive the gluten challenge.

[figure not shown]

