The threshold of VH:CD to receive gluten challenge was initially 2 (protocol version 1) and subsequently 1.8 (protocol version 2) before the final threshold of 1.5 VH:CD was adopted in protocol version 3. The population of subjects who received gluten challenge and had pre/post biopsies, a majority of the patients, will represent the per protocol population 1 (PP1) and will be analysed for the primary and secondary endpoints separately from the subjects who did not receive gluten challenge and had pre/post biopsies, a small fraction of the subjects who will represent the per protocol population 2 (PP2). All primary and secondary endpoints will be analysed in PP1 and PP2 separately.

All subjects will complete the BSFS at the time of each bowel movement from baseline (Visit 1, Week 0/Day 0) up to the final study visit (Visit 8, Week 16/Day 112). Subjects will complete the CeD PRO daily from baseline up to the final study visit. Subjects will also complete the GSRS at screening and, thereafter, weekly from baseline through the final study visit. The BSFS, GSRS and CeD PRO will be completed using a handheld electronic diary at times specified in [Appendix 1](#).

Safety will be monitored on an ongoing basis and subjects may undergo unscheduled visits for safety reasons, if needed. Safety will be assessed throughout the study by clinical laboratory tests, physical examination, vital signs, and AE monitoring.

[Figure 1](#) represents a schematic drawing of the study periods and visits.

Figure 1 CELIM-NRCD-001 study schematic

4 Randomisation

Randomisation, i.e. the random allocation of treatments to subject numbers, will be performed according to the design of the study. A detailed description of the randomisation method, including the size(s) of randomly permuted blocks used to balance the randomisation, will be stored at the restricted area of StatFinn server, where only the randomisation expert and the unblinded statistician will have access to. Once the data base is locked and the treatment code open, the randomisation documents will be moved to the non-restricted area.

Subjects will be randomized at a 1:1:1 allocation to receive 150 mg AMG 714 or 300 mg AMG 714, or placebo once every two weeks for a total of six administrations over ten weeks. Randomization will be stratified by site and sex.

5 Statistical hypotheses

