The GSRS is a 15-question 7-scale questionnaire used to assess five dimensions of gastrointestinal syndromes: diarrhea, indigestion, constipation, abdominal pain and reflux (Svedlund *et al* 1988). While not specific for celiac disease, the GSRS is widely used in gastroenterology and has been used in several clinical trials of experimental medications in celiac disease, thus becoming a very useful tool with abundant existing reference data (Kelly *et al* 2013; Lähdeaho *et al*, 2011; Leffler *et al*, 2015).

Subjects will be asked to complete this questionnaire weekly, using an electronic diary, from the Screening through the Final Study Visit (i.e. on Screening and Visits 1 to 9).

The total GSRS score will be calculated as the sum of the scores of all 15 questions, with the scores for the individual questions between 1 (No discomfort at all) and 7 (Very severe discomfort). Therefore, the smaller the total GSRS score, the milder the symptoms of the subject.

The relative (%) change from baseline in total GSRS score will be analysed using a linear mixed effects repeated measures model (MMRM) with the baseline value, treatment group, site, sex, time point and a time point-by-treatment group interaction term as fixed effects with an underlying correlation structure between the time points that results in the best fit for the model. Subject will be included as a random effect. The following model will be fitted:

$$Y_{ijklm} = \mu + \tau_j + \varphi_k + \alpha_l + \gamma_m + \lambda_{lm} + \beta \cdot \text{baseline GSRS}_{ijklm} + \eta_i + \varepsilon_{ijklm},$$

where

Y_{ijklm} is the relative (%) change from baseline in total GSRS score for subject i ($i = 1, \dots, n_{jkl}$) from site j ($j = 1, 2, 3$), sex k ($k = 1, 2$) and treatment group l ($l = 1, 2, 3$) at week m ($m = 1, \dots, 16$),

μ is the overall mean,

α_l is the fixed effect due to treatment l ,

φ_k is the fixed effect due to sex k ,

τ_j is the fixed effect due to site j ,

γ_m is the fixed effect due to week m ,

λ_{lm} is the fixed interaction effect due to treatment l and week m ,

β is the parameter estimate of the baseline total GSRS score,

η_i is the random effect due to subject i ,

ε_{ijklm} is the random error for subject i from site j ($j = 1, 2, 3$), sex k ($k = 1, 2$) and treatment group l for week m .

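### For GSRS and CeD-GSRS, a missing Week 0 score is replaced by a post-dose score as baseline, although a pre-dose screening score is collected

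*SAP*

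**What the plan says.** SAP section 7.2.1 defines absolute and relative change as the post-baseline value minus a pre-dose value, the relative form being divided by that pre-dose value. After each formula it sets the same order for weekly scores. Week 0 is the baseline, and "If Week 0 score is not available, the first non-missing result within 2 weeks of treatment will be used as baseline". If no such score exists, "Otherwise, the given subject will be considered non-evaluable for the specific test". Screening is admitted only at the end: "In case pre-dose value doesn't exist (i.e. for biopsy endpoints), screening value will be used as baseline".

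Section 3 states: "Subjects will also complete the GSRS at screening and, thereafter, weekly from baseline through the final study visit". Section 7.6.2 builds CeD-GSRS from ten of the fifteen GSRS items, so CeD-GSRS also has a screening score.

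The models in section 7.6.2 take change from baseline at Weeks 1 to 16 as the response: relative for GSRS with absolute as a secondary approach, and absolute for CeD-GSRS. Both include the baseline score as a covariate, and treatment contrasts are estimated from Week 1 onwards.

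**The concern.** A baseline should precede treatment. Here the substitute follows the first dose, which conflicts with the section's own formula and leaves the programmer with a formula and a rule that disagree. Three things follow for an affected subject:

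- The score serves as both baseline and outcome in the same week, so that week's change carries no information.
- Every later change is measured from a value obtained on treatment.
- The covariate used for adjustment is a post-randomisation variable.

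GSRS and CeD-GSRS are named secondary endpoints. What is at stake is a clean definition of their change from baseline and, if the drug acts early, a small distortion of their treatment contrasts.

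**Working it through.** The SAP states no figure for this rule, so there is none to reproduce. The check is of timing, then algebra, then a simulation on assumed inputs.

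**1. Is the substitute post-dose?** Section 4 has study drug given "once every two weeks for a total of six administrations over ten weeks", and section 3 puts the last dose on Day 70. First dose: 70 − 5 × 14 = Day 0. GSRS is weekly from baseline, so the first scores after a missing Week 0 are Week 1 and Week 2, both after the first dose. By section 3, subjects eat placebo gluten from Day 1 and switch to active gluten at Visit 2 (Week 2/Day 14). A Week 1 substitute is therefore post-dose but pre-challenge, and a Week 2 substitute falls at the switch.

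**2. The substituted week.** Change in week w is Y_w − B. If B = Y_w, the change is 0, both absolute and relative. Weeks 1 to 16 are all modelled and no rule removes the row. With share f substituted and drug effect d in that week, the unadjusted contrast for that week falls from d to (1 − f)·d. For f = 20% and d = 0.25 SD this is 0.80 × 0.25 = 0.200 SD (simulated: 0.199).

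**3. Later weeks.** For a true later difference D on the absolute-change scale, affected subjects contribute D − d and the others D. The unadjusted contrast is (1 − f)·D + f·(D − d) = D − f·d. For relative change the substitute also enters the denominator, so f·d is only a guide there.

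**4. Size.** The SAP gives neither f nor d. Assumed: f = 5%, 10%, 20%; d = 0, 0.25, 0.5 SD at Week 1; Week 12 effect 0.50 SD; within-subject correlation 0.6. The simulation used 400,000 subjects per arm, absolute change and a Week 1 substitute. The Monte Carlo standard error of an unadjusted contrast is about √(2 × 0.4) × √(2/400,000) = 0.002 SD. Entries are the Week 12 contrast in SD, unadjusted / adjusted for the baseline covariate.

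| f | d | SAP rule | Screening as fallback |
|---|---|---|---|
| 5% | 0 | 0.500 / 0.499 | 0.500 / 0.499 |
| 5% | 0.25 | 0.487 / 0.492 | 0.500 / 0.500 |
| 5% | 0.5 | 0.473 / 0.484 | 0.497 / 0.498 |
| 10% | 0 | 0.499 / 0.499 | 0.499 / 0.499 |
| 10% | 0.25 | 0.479 / 0.490 | 0.503 / 0.504 |
| 10% | 0.5 | 0.452 / 0.471 | 0.501 / 0.501 |
| 20% | 0 | 0.501 / 0.500 | 0.501 / 0.501 |
| 20% | 0.25 | 0.448 / 0.469 | 0.499 / 0.500 |
| 20% | 0.5 | 0.396 / 0.439 | 0.497 / 0.498 |

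The unadjusted loss tracks f·d (for example, 10% × 0.5 = 0.05 against 0.500 − 0.452 = 0.048). Covariate adjustment, which the SAP models include, reduces it. With d = 0 there is no shift. The screening fallback returns about 0.50 throughout.

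**The case against.** The best defence is the run-in. The endpoint is attenuation of gluten-induced symptoms, and until Week 2 there is no protocol gluten to attenuate. The fallback window largely coincides with that period, a Week 1 score shares the placebo-foodstuff conditions from which the challenge departs, and screening is further away in time. The forced zero is one of 16 weekly rows per affected subject, about 0.6% of rows if 10% are affected (0.10/16). The biopsy rule is no precedent either, because no Day 0 biopsy exists by design.

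Much of this stands. It limits the likely size, and it means that choosing screening has a price. It does not justify a post-randomisation value serving as both covariate and outcome, nor does it resolve the conflict with the pre-dose formula.

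It could also be said that the window does not literally say after treatment. With Week 0 as the dosing visit and weekly scores from then on, after is the natural reading. If before was meant, the SAP should say so.

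Three stronger inferences are tempting but unsupported:

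- **The bias runs in one direction.** It follows the sign of d, which the SAP does not give and which may be zero during the run-in.
- **Screening is a cost-free substitute.** It is further from the challenge than Week 0.
- **The same repair works for CeD PRO.** That diary starts at baseline, so the SAP documents no earlier score to use or impute from. Its models also take the score itself, not its change, so the forced-zero argument does not reach them. The post-dose covariate and the tabulated change from baseline remain.

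**Conclusion.** The point holds as a minor defect in the definition of the GSRS and CeD-GSRS baseline. Three parts follow from the text under the natural reading of the window: the conflict with the pre-dose formula, the exact zero in a modelled week, and the post-randomisation covariate.

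The effect on later contrasts is conditional: about f·d on absolute change, somewhat less after adjustment, and nil without a drug effect in the run-in. On the assumed inputs the adjusted Week 12 loss runs from nothing at d = 0 to 0.061 SD (0.500 − 0.439) at f = 20% and d = 0.5 SD. At f = 10% and d = 0.25 SD it is 0.010 SD. All of these rest on an assumed missing share, early effect and correlation.

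A reader should not infer any doubt about the primary result. VH:CD and the other biopsy endpoints take screening as baseline, and the bowel-movement count model has no baseline term.

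**What to change.** In section 7.2.1, under both change formulas, define the GSRS and CeD-GSRS baseline as the last non-missing score before first dose: Week 0, else screening. This agrees with the formula as written. It also keeps subjects with a screening score who would otherwise be non-evaluable for want of any score in the first two weeks.

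Where no pre-dose score exists and a post-dose fallback is kept, including for CeD PRO, exclude that time point as an outcome for the subject and add a sensitivity analysis without those subjects.

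The cost is a sentence or two and a small change to the derivation program, with no new data. The downside is that a screening baseline lies further in time from the challenge than Week 0, so reporting how many subjects per arm rely on it would be sensible.
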